### **Phase 3: Randomized Controlled Trial**

We will conduct similar qualitative, descriptive, and EMA analyses as noted in the open trial. We will calculate effect size estimates to characterize between group differences and the associated 95% CIs, to understand the precision, or lack thereof, of our estimates.

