**Pilot study in a partial hospital.** Participants ( $n = 65$ ) met criteria for a range of diagnoses, and 70% met criteria for moderate or high suicide risk on the clinician-administered MINI (specific suicide plans and suicidal gestures and attempts). The average number of prior hospitalizations was 2 (range 0 to 20). This pilot study did not include a measure of functional impairment; however, a prior sample from the same partial hospital reported significant disability on the Sheehan Disability Scale ( $M = 7$  (out of 10) for each domain).

**Does interpretation bias matter in a hospital population?** Almost all prior studies of interpretation bias have compared a healthy control group to a psychopathology group; thus, we first examined the clinical relevance of interpretation bias *within* a SMI sample. Even in a restricted range of high symptom severity in our partial hospital, robust associations were found with interpretation bias. Controlling for baseline symptom severity, **patients who endorsed fewer benign interpretations at admission were less likely to respond to treatment** (defined as "very much improved" on the self-reported Clinical Global Improvement Scale), and this model **accounted for 28% of the variance in treatment response**. Interpretation bias upon admission also prospectively predicted **suicidal ideation at discharge** better than any other demographic or clinical variable.

**Randomized Controlled Trial.** Patients were randomly assigned to CBM-I or a neutral control condition. All individuals received treatment as usual at the partial hospital. Patients completed the 10-minute task each day they attended the partial hospital on a laptop computer.

Assessments of interpretation bias and symptoms occurred upon admission and discharge.

**Feasibility and acceptability:** 99% of participants completed daily sessions of CBM-I. Attrition rate for the discharge assessment was low (11%), typically due to inpatient hospitalization or an

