### **Phase 3: Randomized controlled trial.**

In this Randomized Control Trial, we will recruit 64 partial hospital patients. All inclusion and exclusion criteria, sources of subjects, and recruitment methods are the same as detailed in the Phase 2: Open Trial, except that current/active suicidal ideation criteria will be removed, such that individuals with all scores for phq9 item 9 are eligible. Further, after reaching our initial recruitment goal of 64, we will continue to recruit those participants that identify as BIPOC in order to achieve our proposed percentage of BIPOC participants.

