### **Procedures under proposed protocol:**

The research coordinator or another member of the study staff will approach potentially eligible patients on their second day in the program and inform them about the study. During the Open Trial patients approached scored above a 9 on PHQ-9 or GAD-7, PHQ-9 item9 < 2 and they consented to main BHP study. During the RCT patients approached scored above a 9 on PHQ-9 or GAD-7 and had no criteria for PHQ-9 item 9 and can consent to main study at any time prior to consenting to the current study. Interested patients will then receive a detailed description of the study procedures, risk, and benefits and will review a study fact sheet for remote consent with trained study staff. They will then complete the interpretation bias assessment to determine eligibility to participate in the trial.

**Randomization.** We will use MINIMPY software to randomize participants to HabitWorks or Symptom Tracking. MinimPy is a desktop application program for sequential allocation of subjects to treatment groups in clinical trials by using the method of minimisation (<https://sourceforge.net/p/minimpy/wiki/Home/>).

We will enter age and baseline level of interpretation bias as variables for which the program will balance group assignment. The PI will randomize all participants following their eligibility session.

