Demog. Form, CEQ	X				
PHQ-9; GAD-7	X	X	X	X	X
Q-LES-Q, BHS, CFI, MPS, GSE	X		X	X	X
Exit Questionnaire				X	
WSAP	X	X	X	X	X
Scenario Recognition Task				X	
EMA PANAS	X	X	X	X	X
CSSRS- Self Report	X			X	X
System Usability Scale- HW condition				X	
TWEETS- HW condition				X	

The Scenario recognition task is the most widely used assessment of interpretation bias in CBM- and will ensure that effects are not solely attributable to practice or method effects. In brief, participants first read 10 ambiguous scenarios and a comprehension question to ensure they actually read the scenario. In the second phase, participants read the title of the ambiguous scenario followed by four versions of the final sentence presented in a random order. Sentences represent a) a possible positive interpretation, b) a possible negative interpretation, c) a positive foil, and d) a negative foil.

Participants rate each sentence for its similarity in meaning to the original story using a 4-point scale ranging from 1 (very different in meaning) to 4 (very similar in meaning). We will calculate the average similarity rating for negative and positive interpretations.

Co-primary clinical outcomes will include stake-holder relevant measures of global improvement and functioning. The PI will train study staff to administer these brief scales and will monitor reliability using established procedures at the BHP.

Clinician-administered Clinical Global Improvement Scale (CGIS) to assess global improvement.

Clinician-rated 5-item Work and Social Adjustment Scale (WSAS) to assess interference caused by the patient's symptoms in the domains of work, home management, leisure, and family relationships.

Other self-report measures will include:

Credibility Expectancy Questionnaire to assess patients' beliefs about the treatment expectancy (affectively based) and treatment rationale credibility (cognitively based).

Exit Questionnaire to assess patients' satisfaction with the treatment provided.

Beck Hopelessness Scale (BHS) to assess negative attitudes about the future.

Cognitive Flexibility Inventory: The Cognitive Flexibility Inventory is a measure of mental flexibility and assesses the degree to which individuals are able to replace maladaptive thoughts with adaptive ones and maintain a balanced mindset.

15-Item Multidimensional Perfectionism Scale (short form): The MPS is a widely used self-report measure of perfectionism.

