### **Phase 3: Randomized Controlled Trial**

We will recruit 84 participants for the RCT with optional assessments at pre-, post-, 1-month and 3-month timepoints. Follow-up assessments at the 1-month and 3-month timepoints will be considered optional for participants. In this RCT we will randomize individuals to receive the experimental condition HabitWorks or a Symptom Tracking condition. Those in the HabitWorks group will complete the CBM task via smartphone application as an augmentation to treatment as usual (TAU), while those in the Symptom Tracking Group will complete weekly symptom monitoring surveys as an augmentation to TAU.

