### Phase 2: Open Trial

The primary aims of this treatment development project are to develop: a) HabitWorks, b) procedures for hospital augmentation and bridge to outpatient care, and c) procedures for a subsequent RCT. First, we will analyze qualitative data obtained from post-treatment interviews and exit questionnaire. The PI will content analyze audio recordings using a rapid coding technique. Audio recordings will then be transcribed verbatim and analyzed with more conventional analytic methods. Using the constant comparison method from grounded theory transcripts will be read for emerging themes. After independently categorizing thematic clusters, the scientific team will create a coding scheme to organize data, prepare a written report detailing the emerging themes, and discuss results with the advisory board.

We will compare outcomes to a **priori target outcomes** (see Table) after each iteration of the open trial. We will calculate descriptive statistics (e.g., mean, frequencies) to evaluate whether the target outcome was met. When the target is not met, this will prompt a discussion with the team and advisory board about potential modifications. We will calculate effect size estimates to characterize pre-post differences (open trial) and the associated 95% CIs, to understand the precision, or lack thereof, of our estimates.

Target Outcomes	
Target Engagement:	75% of HabitWorks group moves into normal range  of interpretation bias (Benign endorsement = 70%; Negative endorsement = 30%) on the WSAP and on the Scenario Recognition Task ( Similarity rating (1 to 4) for target sentences: benign = 2.3; negative = 1.9).
Treatment Credibility & Expectancy:	Average = 5 (moderate credibility or 50% expectancy)
Retention:	75% of participants complete the 3 month-assessment 75% of participants complete HabitWorks daily during acute treatment 50% of participants complete HabitWorks 3x week in transition phase
Satisfaction:	Average rating 5 or above (on a 1 to 7 scale) on the Exit Questionnaire
Treatment response:	50% of HabitWorks group responds to treatment (“much or very much improved” on CGIS) and 20% reduction in functional impairment in HabitWorks group with a clinically meaningful between group effect size of $d = .40$

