**Power analysis.** One goal of the current project is to determine the recruitment rate at our site, and to compare it to the rate needed for an adequately powered RCT (i.e., 4 individuals per month = 200 participants over 50 months (estimated recruitment duration of a subsequently proposed RCT)). Our primary hypothesis for the subsequent RCT is that HabitWorks will be superior to control on our primary outcomes. We determined that a clinically significant difference for a low-intensity, augmentation treatment is an effect size of  $d = .40$ , which corresponds to a post-treatment between-group difference of 2.8 points on the WSAS. We conducted preliminary power analyses using these numbers and a 15% dropout rate (based on our pilot studies). We estimated that a sample size of 200 would give us >80% power to detect a group difference of  $d = .40$ . This effect appears feasible, given that our pilot RCT resulted in a between-group effect size of  $d = .63$  on a measure of well-being.

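### Adjusting the Phase 3 arm comparison for Pre scores and the minimisation factors would give a modest, conditional gain in precision from data already collected

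*SAP*

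**What the plan says.** The between-arm analysis is a single sentence in the SAP (VI, Phase 3): "We will calculate effect size estimates to characterize between group differences and the associated 95% CIs". The other analyses carried over from the open trial are qualitative, descriptive and EMA; none supplies a baseline covariate for the arm contrast.

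The results will be read against d = .40. The SAP's Target Outcomes table asks for a "20% reduction in functional impairment in HabitWorks group with a clinically meaningful between group effect size of" .40, and its Power analysis paragraph says that this d "corresponds to a post-treatment between-group difference of 2.8 points on the WSAS". Neither place names an SD.

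The baseline data are already in the protocol. Under Randomization: "We will enter age and baseline level of interpretation bias as variables for which the program will balance group assignment". The Schedule of Assessments marks Pre for the WSAS, WSAP, PHQ-9, GAD-7, Q-LES-Q and several other scales. It does not mark Pre for the CGIS or the Scenario Recognition Task. On the main outcomes the protocol (Measures) says: "Co-primary clinical outcomes will include stake-holder relevant measures of global improvement and functioning"; these are the CGIS and the WSAS. So one co-primary outcome has a Pre score and the other has none.

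**The concern.** The SAP gives the intervals so that readers can see how precise the estimates are, and the estimates are meant to support a later, fully powered trial. In a sample this small, a baseline measurement of the same scale is usually the cheapest source of extra precision, and here it is collected but not used.

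The minimisation factors raise a related point. If a factor that is balanced by design also predicts outcome, an interval that ignores it tends to be too wide. The protocol's own pilot makes this plausible for interpretation bias: after control for baseline severity, "patients who endorsed fewer benign interpretations at admission were less likely to respond to treatment".

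At stake is the width of the interval around d, and whether the d that is reported can be compared with the .40 target.

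**Working it through.** **The plan's own figure.** d = .40 and 2.8 WSAS points imply an SD of 2.8/.40 = 7.0. This is a planning value for the later trial, used here only to convert d into WSAS points.

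**Inputs.**
- Recruitment: 64 (Protocol III, Phase 3: "we will recruit 64 partial hospital patients") or 84 (Protocol V, Phase 3: "We will recruit 84 participants for the RCT"). Both are carried through.
- Loss: 15% dropout (SAP, Power analysis, stated for the later trial) or 75% retention (SAP, Target Outcomes, for the 3-month visit).
- Analysed n: 64 × .85 = 54.4; 84 × .85 = 71.4; 64 × .75 = 48; 84 × .75 = 63.
- Assumed, because the documents do not give them: 1:1 allocation, and a correlation r between Pre score and outcome of .3, .5 or .7.

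**Formulas** (95% half-width for d, standardised by the unadjusted SD, at d = .40):
- Unadjusted: 1.96 × √(4/n + d²/(2n)).
- ANCOVA with three covariates, of which only the Pre score is prognostic: 1.96 × √((1 − r²) × (4/n) × (1 + 3/(n − 6)) + d²/(2n)). The factor 1 + 3/(n − 6) is the cost of estimating three covariates.

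**Worked example** (n = 54.4, r = .5): 4/n = 0.0735, d²/(2n) = 0.0015, cost factor 1.062. Unadjusted: 1.96 × √0.0750 = 0.537. Adjusted: 1.96 × √(0.75 × 0.0735 × 1.062 + 0.0015) = 1.96 × √0.0600 = 0.480.

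| Recruited, loss | Unadjusted | r = .3 | r = .5 | r = .7 |
|---|---|---|---|---|
| 64, 15% dropout | 0.54 | 0.53 | 0.48 | 0.40 |
| 84, 15% dropout | 0.47 | 0.46 | 0.42 | 0.35 |
| 64, 75% retained | 0.57 | 0.56 | 0.51 | 0.43 |
| 84, 75% retained | 0.50 | 0.49 | 0.44 | 0.37 |

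In WSAS points at 15% dropout, 1.96 × 7 × √(4/n) gives 3.7 (N = 64) and 3.3 (N = 84) unadjusted. Multiplying 4/n by (1 − r²) and the cost factor gives 3.7/3.3/2.7 and 3.2/2.9/2.4 for r = .3/.5/.7.

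**Where the gain vanishes.** At r = .2 and 15% dropout the adjusted half-width is 0.542 against 0.537 (N = 64), and 0.469 against 0.469 (N = 84). At r = 0 the interval is 2 to 3% wider.

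**Check by simulation** (4,000 trials per setting, n = 54 and 71, true d = .40, t intervals). The adjusted interval was narrower by 1.4/10.8/26.4% and 2.4/11.4/26.8% at r = .3/.5/.7, and wider by 3.1% and 2.3% at r = 0. Coverage was 94.7 to 95.7% throughout.

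**Standardiser, once adjustment is used.** Dividing by the residual SD turns a true d of .40 into .40/√(1 − r²) = .42, .46 or .56. Equivalently, a difference of 2.8 × √(1 − r²) = 2.7, 2.4 or 2.0 WSAS points would then read as .40. Dividing by the unadjusted SD avoids this.

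**The case against.** The strongest reply is that nothing here is wrong. Phase 3 is a pilot, the SAP plans no hypothesis test for it, no passage sets a precision target, and an unadjusted interval is valid. That stands, and it limits the point to a recommended improvement.

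The second reply is that the benefit rests on an unknown, which also stands. Entry is restricted by symptom severity and WSAP accuracy, and intensive treatment falls between Pre and Post, so r = .7 may be optimistic. The pilot finding concerns self-reported global improvement. It does not show that Pre WSAS predicts later WSAS, and it cannot be used to size the gain.

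Third, 15% dropout is borrowed from the later trial, and the 1- and 3-month visits are optional in Phase 3. The 75% rows answer this: the widths grow, but the proportional gain hardly changes.

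Two stronger readings are tempting. A reader might infer that the plan would inflate d by dividing by a residual SD. It would not: the SAP names no model, so that hazard arises only if adjustment is adopted. A reader might also infer, from the protocol's Treatment adherence paragraph, that session count would be a covariate in the arm comparison. That paragraph allows it as a control variable when needed, but it sits in the open-trial section. Although the measures carry over to the RCT, no passage plans such a use. The Symptom Tracking table also lists a session frequency of its own, so a count of zero in that arm cannot be assumed.

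**Conclusion.** The point holds as a modest and conditional gain in precision. Net of the cost of three covariates, the interval narrows by roughly 1 to 3% at r = .3, 10 to 11% at r = .5 and about 26% at r = .7, across both sample sizes and both loss assumptions. It widens by 2 to 3% if no covariate is prognostic. These figures assume 1:1 allocation, a linear relation and a correlation that the documents do not report. They apply to outcomes with a Pre score, such as the WSAS, and not to the CGIS.

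A reader might take the omission to mean that the planned estimates are biased or the intervals invalid. The documents do not support that: randomised allocation makes the unadjusted contrast sound, and ignoring prognostic minimisation factors errs towards an interval that is too wide. The SAP should be amended because the change uses data already collected and settles the covariates and the SD before results are seen.

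**What to change.** Add to the SAP's Phase 3 paragraph:

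> For continuous outcomes with a Pre score, the between-arm difference at each visit will be estimated by ANCOVA adjusted for the Pre value of that outcome, age, and the same baseline interpretation-bias score used in the minimisation (entered once when it is itself the Pre value of the outcome), with 95% CI. It will be reported in scale points and as d, dividing by the unadjusted pooled SD of the outcome at that visit, not the residual SD, so that it is comparable with the d = .40 (2.8 WSAS points) target. CGIS has no Pre score and will be adjusted for age and the baseline interpretation-bias score only.

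The SAP should also say which WSAP score the minimisation uses. The protocol derives negative endorsement, benign endorsement and reaction-time scores from the task, and uses accuracy for eligibility.

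The cost is a few sentences and minor programming, with no new data and no added burden on participants. The only statistical downside is the 2 to 3% widening if the covariates turn out not to be prognostic.
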